τHHb_{recovery}	Time constant of HHb during recovery from exercise
ABR	ABR form, General Assessment and Registration form, is the application form that is required for submission to the accredited Ethics Committee (In Dutch, ABR = Algemene Beoordeling en Registratie)
AE	Adverse Event
AR	Adverse Reaction
ATP	Adenosine triphosphate
ATT	Adipose tissue thickness
CA	Competent Authority
CCMO	Central Committee on Research Involving Human Subjects; in Dutch: Centrale Commissie Mensgebonden Onderzoek
CK	Creatinine Kinase
CV	Curriculum Vitae
DPF	Differential pathlength factor
DSMB	Data Safety Monitoring Board
EU	European Union
EudraCT	European drug regulatory affairs Clinical Trials
FAO	Fatty Acid Oxidation
FEV₁	Forced expiratory volume in one second
GCP	Good Clinical Practice
HAES	Habitual Activity Estimation Scale
HMP	Hexose monophosphate
IB	Investigator's Brochure
IC	Informed Consent
IMCL	Intra myocellular lipids
IMP	Investigational Medicinal Product
IMPD	Investigational Medicinal Product Dossier
KO	Knock Out
METC	Medical research ethics committee (MREC); in Dutch: medisch ethische toetsing commissie (METC)

MRS	Magnetic Resonance Spectroscopy
NK	Nutritional Ketosis
Nm	Nanometer
O₂	Oxygen
PCr	Phosphocreatine
Pi	Inorganic phosphorus
PPE	Physical performance enhancement
(S)AE	(Serious) Adverse Event
SPC	Summary of Product Characteristics (in Dutch: officiële productinformatie IB1-tekst)
Sponsor	The sponsor is the party that commissions the organisation or performance of the research, for example a pharmaceutical company, academic hospital, scientific organisation or investigator. A party that provides funding for a study but does not commission it is not regarded as the sponsor, but referred to as a subsidising party.
SUSAR	Suspected Unexpected Serious Adverse Reaction
VLCADD	Very Long Chain Acyl-CoA Dehydrogenase Deficiency
Wbp	Personal Data Protection Act (in Dutch: Wet Bescherming Persoonsgegevens)
WMO	Medical Research Involving Human Subjects Act (in Dutch: Wet Medisch-wetenschappelijk Onderzoek met Mensen)
WOB	Work of breathing

SUMMARY

Rationale: Very Long-Chain Acyl-CoA Dehydrogenase deficiency (VLCADD) is a rare inborn error of fatty acid metabolism with a broad clinical presentation ranging from infant fatality to exercise intolerance and elevated risk of exertional rhabdomyolysis with onset in childhood or adolescence. These episodes of rhabdomyolysis can result in permanent muscle damage and deterioration of activity level of adult patients. We recently obtained evidence that these symptoms are in part due to a lower energetic efficiency of upper leg muscle fibers that aggravates reliance on carbohydrate stores in this disease, rendering the organ vulnerable to an exertional energy crisis (Diekman et al, PloS One 2016). While no effective treatment has been available for VLCADD, it has long been proposed that nutritional ketosis (NK) could be highly beneficial to patients. Amongst others, ketone bodies could take on the role of primary energy source in exercising muscle. The problem has been that, until now, no vehicle for establishing NK in humans without undesired side effects has been available. A breakthrough has finally been achieved by collaborator [name] in Oxford whose team has recently produced an edible ketone ester that can achieve acute NK in human subjects via oral ingestion without any undesired side-effects. It was found that the ketone ester produced significant physical performance enhancement in rodents and human athletes (Cox et al., *Science* (in review)).

The effect has been attributed to enhanced muscle mitochondrial function in addition to glycogen sparing. Here, we will investigate if acute NK in adolescent and adult symptomatic VLCAD deficient patients can boost muscle mitochondrial function in vivo. If so, a rational basis will have been established for therapeutic use in this metabolic myopathy. This study will include patients from the age of 16 years that could benefit from NK as well. Since rhabdomyolysis often has an onset in adolescence, confirmation of our hypothesis would lead to therapeutic use in that age group as well. Moreover, older patients often suffer from severe exercise intolerance and loss of muscle function due to earlier episodes of rhabdomyolysis, leaving most of them unable to complete our study protocol. Due to the rarity of the disease and earlier argumentation, it's vital to include adolescent subjects to reach sufficient power in this study. As such, this study constitutes a vital first step towards possible validation of an effective treatment for patients with VLCADD that may improve the quality of life including an active lifestyle with overall health benefits.

Objective: To test if acute NK boosts muscle mitochondrial function in vivo in patients with VLCADD in order to establish a rational basis for therapeutic use in this disorder. A secondary objective is to gather data to test the working hypothesis that the positive effect of acute NK on muscle mitochondrial function results from enhanced substrate supply to the tricyclic acid (TCA) cycle.

Study design: randomised, blinded, placebo controlled, 2-way cross over trial.

Study population: Six Patients with VLCADD between 16 and 65 years of age, seen for evaluation in the VLCADD expertise centre of the UMC Utrecht.

Intervention (if applicable): Oral intake of nutritional drinks; prolonged moderate-intensity exercise on bicycle ergometer; in vivo Magnetic Resonance Spectroscopy; muscle microbiopsy; venipuncture.

Main study parameters/endpoints:

- Whole body:
 - Physical performance during a 45 bicycle exercise test at individual FATMAX workload (typically of the order of 40%MVO₂). Specifically:
 - completion of 40 min upright exercise bout at FATMAX workload (yes/no; if no, #minutes)
 - completion of 5 min in-magnet exercise bout at FATMAX workload (yes/no; if no, #minutes)
 - subjective fatigue and muscle ache score after each exercise bout (scale 0-10) and 24 hours after session (telephone consultation)
 - HAES score questionnaire
- Muscle:
 - resting quadriceps phosphocreatine (PCr) and inorganic phosphate concentrations; pH
 - exercise quadriceps phosphocreatine (PCr) and inorganic phosphate concentrations; pH
 - post-exercise rates of recovery of quadriceps PCr, Pi and pH
 - optional: resting and post-exercise muscle levels of glycogen, lactate, 3-OH butyrate, and (very) long (C18-C14) to medium (C12-C8) to short chain (C6-C2) acetyl-carnitines (on a patient-voluntary basis)
- Blood:
 - levels of 3-OH butyrate, glucose, bloodgas, lactate, acylcarnitines and creatine kinase at rest and post-exercise
- Urine: myoglobine

Nature and extent of the burden and risks associated with participation, benefit and group relatedness: In clinical practice, many patients with VLCADD wonder to which extent they are able to exercise safely. Any means of boosting this capacity will greatly improve the quality of life and long-term health in this patient population. Acute nutritional ketosis after ingestion of a novel edible ketone ester is a very promising novel therapy towards this aim and has already been tested with positive effects in human athletes. This study will gain insight whether a sound metabolic basis exists for its therapeutic use in this patient population.

Patients will be asked to participate in three study sessions:

session I (site: nearest Academic Medical Center, Pediatric test ward).

- standard maximal cardiopulmonary exercise test (CPET; bicycle ergometry with indirect calorimetry)

objective: determination of VO_{2max} in order to set the desired exercise workload of maximal individual rate of fat oxidation (FATMAX; typically ~40% MVO_2) in sessions 2 and 3.

- venipuncture

objective: measure basal metabolic profile and rise in blood lactate and CK levels in response to CPET.

sessions II and III (site: Neuroimaging Magnetic Resonance Center UMC Groningen).

- venipuncture + cannulation

objective: prepare subject for serial (every 10 min) blood sampling for off-site metabolic profiling

- oral intake of nutritional drink A or B (ketone and placebo drinks, respectively)

Each subject will receive both drinks over the course of the trial in a blinded fashion – i.e., if drink A in session II, then drink B in session III, and vice versa.

- microbiopsy from the quadriceps muscle (optional)

1st biopsy: 20 min after oral drink; 2nd biopsy: immediately following end of exercise bout 1. objective: metabolomic profiling of the state of the energy metabolic network in muscle and mapping of individual phenotypic muscle properties (fiber type, mitochondrial density, capillary density). Biopsies will be obtained from the m. vastus lateralis of the left leg. Hereto, a preparatory superficial incision of the skin and fascii will be made under local sedation and bandaged, allowing fast and reproducible biopsy sampling prior to and immediately following exercise bout 1 below.

- 40 min upright bicycling exercise at FATMAX outside MR scanner (exercise bout 1)

Blood samples are collected every 10 minutes.

- microbiopsy from the quadriceps muscle (optional)

Biopsy will be obtained from the m. vastus lateralis of the left leg (see above).

- 5 min supine bicycling exercise at 50% MVO_2 inside MR scanner (exercise bout 2)

*serial in vivo ^{31}P MR spectra will be recorded non-invasively from the m. vastus lateralis of the right leg as previously (protocols **12-211/K** (VLCAD; UMC Utrecht); **NL41313.042.12** (MCAD; UMG) to determine energy and proton balance in the muscle during exercise and the kinetics of metabolic recovery following exercise. A blood sample will be taken after the subject has exited the scanner room. Final blood samples including on-site analysis of CK levels are taken up to 3 hr post-session III to monitor any rhabdomyolytic event.*

- 24 hours after session II and III, co-investigator [name] will call each subject to evaluate subjective fatigue and muscle complaints after the subject left the test facility.

Time between study sessions I and II will be at least 7 days; time between study sessions II and III will be 7 days. For session I, patients will be asked to abstain from food 3 hrs prior to the test. For sessions II and III, participants will be asked to keep a 'food diary' for the week prior to the test in order to monitor the caloric intake and macronutrient content of each participant. For sessions II and III, patients will travel to Groningen the evening prior to the study and will be housed in a hotel across the street from UMCG. Patients are able to take a

late evening snack or meal of their choice in correspondence with their individual record of maximal fasting duration, given a start time of the study at 08:00 am the following day. Patients will be allowed the same light breakfast according their normal diet before they will receive the caloric drive before the test. The breakfast will be the same for session II and III.

No adverse effects of this study are expected. Of the listed interventions that are proposed here, all but one – i.e., ingestion of the ketone caloric drink - have previously been included and approved in clinical investigations of metabolic myopathy patients by members of the investigative team in Amsterdam, Utrecht and/or Groningen: venipuncture and microbiopsy of the quadriceps muscle prior to and after exercise (protocol 04/1984 (MCADD; AMC Amsterdam); protocol **NL41313.042.12 (MCADD; UMCG)**); bouts of prolonged bicycle exercise outside and inside a MR scanner including in vivo MR spectroscopic data collection (protocol **12-211/K (VLCADD; UMC Utrecht; protocol NL41313.042.12 (MCADD; UMCG)**).

Of the interventions, only the **burden** of collecting tissue samples from the quadriceps muscle by microbiopsy is rated as moderate (as opposed to ratings of nil to minor burden for all other interventions¹). As such, this intervention will only be performed on a voluntary basis; it will not affect enrollment in the study. Muscle tissue sampling is, however, needed – and therefore desirable - to test the secondary hypothesis that NK boosts muscular mitochondrial function specifically at the level of substrate supply to the TCA cycle. Without the biopsy data, this secondary hypothesis cannot be validated. It would be highly desirable to know the outcome of that test since the information is needed to develop a proper mechanistic understanding of any therapeutic value of ketone administration in human metabolic myopathies such as fatty acid oxidation defects. On these grounds, the burden of microbiopsy is considered justifiable.

The **safety** of the nutritional drinks that will be administered and the expected acute, transient mild ketosis (concentrations of ketone bodies < 3 mM) has been thoroughly tested and documented in healthy subjects (see references 9,10). The drink has been designated as 'GRAS' (= Generally Recognized as Safe) by the Federal Drug Administration of the

¹ the short, maximum exercise test in session I will use anaerobic derived energy. As patients with VLCADD do not have a problem in glycolysis, the burden for this test will be nihil. The endurance test at submaximal level might induce muscle pain temporarily. the burden for patients is classified as minimal and patients will be monitored accordingly during the study period. Blood will be drawn intravenously from patients; this implies a minimal burden.

United States allowing it to be used as a foodstuff in the USA. No particular risk for VLCADD patients is expected with respect to oral ingestion of the ketone ester since its metabolites are natural, organic compounds released without any caution or proton load that are readily oxidizable by cellular mitochondria irrespective of enzymatic defects in fatty acid oxidation.

The **benefit** to VLCADD patients of participation in the study is potentially enormous. In our previous applications for exercise and MRS testing in metabolic myopathy (protocols **12-211/K (VLCAD)**; UMC Utrecht) and **NL41313.042.12 (MCAD)**, respectively), we put forward that the benefit of those studies would be that it would help establish a platform to conduct studies on the effectiveness of medication. Here, we now exploit this validated platform to test the metabolic effects of a nutritional drink that may revolutionize therapy of human metabolic myopathies due to defects in carbohydrate or fat metabolism. Ultimately, an effective treatment for VLCADD may be available for the first time to improve the quality of life of patients, including the opportunity to engage in a more active lifestyle with generic (including cardiovascular and anti-diabetic) health benefits.

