In vivo ³¹P MRS read-out of muscle mitochondrial performance

Phosphorus magnetic resonance spectroscopy (³¹P MRS) allows for non-invasive read-out of intramuscular pH and concentrations of Pi, PCr and ATP in human tissues (17). As such, dynamic ³¹P MRS recording of these metabolic variables in muscle offers a window onto the integrated *in vivo* performance of the cellular metabolic networks that produce ATP from the breakdown of fat and carbohydrates to maintain energy balance during exercise. ³¹P MRS-derived parameters such as the rate constant of PCr and Pi recovery post-exercise offer unsurpassed indices of *in vivo* mitochondrial function that have proven most useful in the clinical investigation of human metabolic myopathy (17). Recently, we applied this method to investigate energy balance in quadriceps muscle of VLCADD patients during an endurance exercise task (Diekman, manuscript in preparation). We found no evidence for impaired mitochondrial ATP synthetic function. However, changes in Pi and PCr during a standardized in-magnet bicycling exercise test were threefold larger than in healthy controls suggesting lower contractile efficiency of VLCADD muscle. Such a muscle phenotypic adaptation would aggravate the problem in VLCADD of exclusive dependence on turnover of the finite muscle carbohydrate store for ATP production, in turn explaining the known elevated risk for exertional rhabdomyolysis in VLCADD (Diekman, manuscript in preparation). Conversely, these results suggest that any boost of muscle mitochondrial function from acute NK should

be an effective therapy to improve exercise tolerance and lower the risk of exertional rhabdomyolysis in VLCADD.

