3. STUDY DESIGN

This is a randomised, blinded, placebo controlled, two-way cross over trial. Patients with VLCADD will be recruited by the VLCADD Expertise Center at UMC Utrecht. Nutritional ketosis will be compared to a placebo, delivered as an isocaloric drink before exercise. An individualised, standardised bicycle exercise protocol will be completed by each participant with collection of blood metabolites, respired gases, and subjective ratings of fatigue and muscle complaints. In addition in vivo ³¹P MR Spectroscopic recordings will be made from the quadriceps muscle before (resting), during and post-exercise. An optional muscle biopsy will be obtained from the quadriceps before and after exercise.

Patients will be asked to participate in three study sessions:

session I (site: nearest Academic Medical Center, Pediatric test ward).

- standard maximal cardiopulmonary exercise test (CPET; bicycle ergometry with indirect calorimetry)
objective: determination of VO_{2max} in order to set the desired exercise workload of maximal individual rate of fat oxidation (FATMAX; typically ~40% MVO_2) in sessions II and III below.
- venipuncture
objective: measure rise in blood lactate and creatine kinase (CK) levels in response to CPET

sessions II and III (site: Neuroimaging Magnetic Resonance Center UMC Groningen).

- venipuncture + canulation
objective: prepare subject for serial (every 10 min) blood sampling for off-site metabolic profiling
- oral intake of nutritional drink A or B (ketone and placebo drinks, respectively)
Each subject will receive both drinks over the course of the trial in a blinded fashion – i.e., if drink A in session II, then drink B in session III, and vice versa.
- microbiopsy from the quadriceps muscle (optional)
*1st biopsy: 20 min after oral drink; 2nd biopsy: immediately following end of exercise bout.
objective: metabolomic profiling of the state of the energy metabolic network in muscle and mapping of individual phenotypic muscle properties (fiber type, mitochondrial density, capillary density). Biopsies will be obtained from the m. vastus lateralis of the left leg. Hereto, a preparatory superficial incision of the skin and fascii will be made under local sedation and bandaged, allowing fast and reproducible biopsy sampling prior to and immediately following exercise bout 1 below.*

- 40 min upright bicycling exercise at FATMAX outside MR scanner (exercise bout 1)

Blood samples are collected every 10 minutes.

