Subjects state subjective fatigue and muscle ache following exercise bout.

- microbiopsy from the quadriceps muscle (optional)

Biopsies will be obtained from the m. vastus lateralis of the left leg (see above).

- 5 min supine bicycling exercise at FATMAX inside MR scanner (exercise bout 2)

*serial in vivo 31P MR spectra will be recorded non-invasively from the m. vastus lateralis of the right leg as previously (protocols **12-211/K** (VLCAD; UMC Utrecht); **NL41313.042.12** (MCAD; UMG) to determine energy and proton balance in the muscle during exercise and the kinetics of metabolic recovery following exercise. Subjective fatigue and muscle ache scores and a blood sample will be taken after the subject has exited the scanner room. Final blood samples including on-site analysis of CK levels are taken up to 3 hr post-session III to monitor any rhabdomyolytic event.*

- 24 hours after session II and III, co-investigator [name] will call each subject to evaluate subjective fatigue and muscle complaints after the subject left the test facility.

Time interval between study sessions I and II will be at least 7 days; between study sessions II and III: 7 days. The night prior to sessions II and III, patients will be housed in close vicinity to the UMCG. Patients will be instructed to take a late evening snack or meal according to their individual record of maximal fasting duration, given a start time of the study at 08:00 am the following day. Patients will be allowed a light breakfast according their normal diet before they will receive the caloric drive before the test. The breakfast will be the same for session II and III.

The total duration of the first session will be around 45 minutes, with 30 minutes of preparation and 8-12 minutes of cycling (exact time length dependent on the maximal endurance of the participant). The total duration of the second and third session will be around 5 hours including 45 minutes of preparation, 45-60 minutes of bicycling for the submaximal endurance exercise test and 3 hours of post-exercise resting where after the last blood and urine sample will be collected. During this 3 hour period, participants will be asked to fill out a HAES diary and can watch a DVD to pass time.

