4. STUDY POPULATION

4.1 Population (base)

Six patients with VLCADD between 16 and 65 years of age, seen by [name] for evaluation in the VLCADD expertise center of the UMC Utrecht.

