8.3 Study procedures

The study is introduced to the patient by co-investigator [name], MD, of the VLCADD expertise center in Utrecht in correspondence with their individual metabolic paediatrician/internist. The study will be announced during the 'patient information day' that's annually held by the the IcFAO expertise centre and by electronic newsletter to which most VLCADD patients or their caretakers are subscribed. Eligible patients will receive an information letter about the study. After a two week consideration period co-investigator [name] will send a reminder letter to subjects who did not respond to the inquiry. This letter will repeat the invitation to participate in the study. If after one more week the subject fails to reply, it is assumed that the subject is not interested and he or she will not be contacted any further. If the subject is interested and has given informed consent, the patient is included in the study, and the subject will be checked for the inclusion- and exclusion criteria The investigator informs the subject about final inclusion, or possible exclusion of the study on basis of the criteria.

Session I: Determination of the VO₂max (CPET) and FATMAX.

Participants are asked to cycle at maximal speed on an ergometric bicycle on a functional test ward at the nearest UMC location (AMC, UMC Utrecht or UMC Groningen). Prior to this session they will be asked to complete a HAES questionnaire containing questions on exercise frequency and the presence of physical complaints during or after exercise.

Sessions II and III.

In the week prior to testing, participants will be asked to keep a 'food diary' for the week prior to the test in order to monitor the caloric intake and macronutrient content of each participant. For sessions II and III, patients will travel to Groningen the evening prior to the study and will be housed in a hotel across the street from UMCG. Patients will be instructed to take a late evening snack or meal in correspondence with their individual record of maximal fasting duration, given a start time of the study at 08:00 am the following day. Patients will be allowed the same light breakfast according their normal diet before they will receive the caloric drive before the test. The breakfast will be the same for session II and III.

Venipuncture and blood sampling:

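### Breakfast is matched across sessions II and III but the late evening meal is not, which leaves a small, avoidable source of within-patient noise in a six-patient crossover

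*Protocol*

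**What the plan says.** Section 3 of the Protocol sets the design: "This is a randomised, blinded, placebo controlled, two-way cross over trial". Section 4.1 sets the size: "Six patients with VLCADD between 16 and 65 years of age". Each patient has the ketone drink in one of sessions II and III and the placebo drink in the other, seven days apart.

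The diet rules before those sessions are:

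- **Evening meal, Summary:** patients may take a "late evening snack or meal of their choice in correspondence with their individual record of maximal fasting duration", given an 08:00 start.
- **Evening meal, section 3:** "Patients will be instructed to take a late evening snack or meal according to their individual record of maximal fasting duration".
- **Evening meal, section 8.3:** "Patients will be instructed to take a late evening snack or meal in correspondence with their individual record of maximal fasting duration".
- **Breakfast, all three places:** "The breakfast will be the same for session II and III".
- **Food diary, Summary and section 8.3:** kept for the week before the test, "in order to monitor the caloric intake and macronutrient content of each participant".

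The Summary alone says the meal is the patient's choice. None of the three sections asks for the same evening meal before both sessions.

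**The concern.** By fixing breakfast, the protocol accepts that diet before the test should be constant within a patient. It stops one meal short.

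Its own rationale makes the omitted meal relevant. Section 1 describes VLCADD muscle as having "exclusive dependence on turnover of the finite muscle carbohydrate store for ATP production". The Summary attributes the ketone effect partly to glycogen sparing, and section 8.1.2 lists muscle glycogen as an optional endpoint. A patient who eats a large carbohydrate meal before one session and a light snack before the other could plausibly start the two exercise bouts in different states.

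The efficiency of a crossover comes from comparing a patient with himself or herself, so variation between sessions is what limits a within-patient comparison. Section 4.4 makes clear that the sample size is set by patient availability. The team cannot readily recruit its way out of noise, so removing avoidable variance is one of the few means it has.

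**Working it through.** **Comparison of the rules.** All three versions of the evening-meal rule refer to the same personal fasting record and the same start time, which should keep the timing of the meal similar in both sessions. Content and amount are left open in all three. The diary would record a difference but is not described as a means of preventing one.

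**No plan figure to reproduce.** Section 4.4 gives no within-patient SD and no power. It says only that differences of 30% or more were detectable in earlier case-control work. The rest is therefore an illustration on stated assumptions.

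**Inputs.** From the Protocol: n = 6, two-sided alpha 0.05 (section 10.2). Assumed: a share f of the variance of the paired difference comes from unmatched meals, and the true effect is 1.25 SD of that difference.

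**Step 1, gain in SD and equivalent sample size.** Matching removes the share f. The SD falls by 1 − √(1 − f), and six matched patients are worth 6/(1 − f) unmatched ones.

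**Step 2, power with a paired t-test** (noncentral t, 5 degrees of freedom). The standardised effect becomes 1.25/√(1 − f).

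| f (assumed) | Fall in SD | Equivalent n | Standardised effect | Power |
|---|---|---|---|---|
| 0 | 0% | 6.0 | 1.25 | 69% |
| 0.1 | 5.1% | 6.7 | 1.32 | 73% |
| 0.2 | 10.6% | 7.5 | 1.40 | 78% |
| 0.3 | 16.3% | 8.6 | 1.49 | 83% |

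**Step 3, power with the planned test.** Section 10.2 plans a Mann-Whitney test, which ignores the pairing and keeps between-patient variance in the error. I simulated normal data, six values per drink, with total variance 1 per session and within-patient correlation ρ before matching. The SD of the difference is √(2(1 − ρ)) and the effect is 1.25 times that. Matching removes 20% of the within-patient variance (f = 0.2).

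| ρ (assumed) | Effect, in single-session SDs | Power unmatched | Power matched | Gain, points |
|---|---|---|---|---|
| 0.3 | 1.48 | 59% | 66% | about 7 |
| 0.5 | 1.25 | 44% | 49% | about 5 |
| 0.7 | 0.97 | 24% | 26% | about 2 |

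The same change that gives about 9 points with a paired t-test (78 − 69) gives about 2 to 7 points with the planned test.

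**The case against.** The strongest reply is that the gap may not matter for the main endpoints. Those are intramuscular Pi, PCr and pH and the recovery rate constants (section 8.1.1). Between the evening meal and the in-magnet measurement come a matched breakfast, an isocaloric drink and up to 40 minutes of cycling at the patient's own workload, so the nearest nutritional inputs are already controlled. The sentence on the carbohydrate store explains the risk of rhabdomyolysis. The same part of section 1 reports no impaired mitochondrial ATP synthesis and points to lower contractile efficiency. Nothing in the protocol shows that the previous evening's intake shifts the MRS measures. This stands: the mechanism is plausible, not demonstrated, and f may be close to zero.

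A reader might also infer more than the documents support:

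- **That patients have free choice throughout.** Only the Summary says so. In every version the meal is tied to the fasting record.
- **That a chance imbalance in meals between the drinks is a second harm, or a bias.** Drink order is randomised and the meal comes before the drink. Chance imbalance is part of the sampling error already counted.
- **That the trial would gain 9 points of power.** That figure needs a paired t-test, which is not the planned analysis.
- **That the diary will go unused in the analysis.** The protocol names no such use and marks multivariate analysis as not applicable (section 10.3), but a descriptive use could stand in an analysis plan that is not shown.

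What survives the reply is that the protocol chose to match diet, left one meal unmatched, and can close the gap with very little effort.

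**Conclusion.** The point holds as a minor one about precision. The evening meal is not repeated within patient, and its content and amount can differ between the two drinks. The documents do not give the resulting loss of precision. The worked gains rest on three assumptions: the share of variance due to meals, the effect of 1.25 SD and, for the planned test, the within-patient correlation. With a meal share near zero nothing is gained. The randomised comparison remains valid either way.

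**What to change.** Bring the Summary, section 3 and section 8.3 to one wording for the evening meal. Leave the individual fasting-duration rule unchanged. Add one sentence: before session III the patient repeats the evening meal recorded in the diary for the evening before session II, in content, amount and approximate time, and any deviation is noted.

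The cost is a small burden on the patient. Compliance would rest largely on self-report: patients stay in a hotel near the site, and no supervised meal is described. No extra visit or measurement is needed.
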